Bone mineral density will be evaluated in all patients at the lumbar spine (L1-L4), femoral neck, and total hip at the Week 24/Baseline, Week 36, and Week 52/Early Termination visits. The absolute, change, and percent change from parent study Baseline and Z-scores will be summarized by visit and parent study treatment group.

The mean percentage change at Week 52 from parent study Baseline in bone mineral density and corresponding 95% CI will be provided for each treatment group. For patients who were randomized to 24 weeks of treatment with relugolix and add-back in the parent studies (Group A in MVT-601-3001 or MVT-601-3002) and enrolled in the extension study, the lower bound of the 95% CI for mean percentage change at Week 52 from parent study Baseline in bone mineral density lumbar spine (L1-L4) will be compared with a pre-specified clinically acceptable threshold of -2.2% to evaluate magnitude of bone mineral density loss after 52 weeks of treatment. If the lower bound is > -2.2%, the relugolix add-back treatment arm will be considered to have successfully prevented bone mineral density loss.

Sample Size Estimation

Because this is an extension study, the sample size will be determined by the number of patients who have completed a parent study (MVT-601-3001 or MVT-601-3002) and who are eligible and willing to participate in the extension study. It is estimated that approximately 600 patients (75% of the total of 780 patients who will be randomized into the parent studies) will participate in this study.

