6.6.2.6. Bone Mineral Density

Bone mineral density is determined using DXA scanning and will be assessed at the lumbar spine (L1, L2, L3 and L4), total hip, and femoral neck (same leg within each patient). Training, quality review, and readings will be done by a central radiology laboratory as described in the central radiology charter for bone mineral density.

Throughout the study, the same DXA apparatus will be used at each site and operated in the same scan mode for all scans for an individual patient, and should be the same as used for the patient during the parent study (MVT-601-3001 or MVT-601-3002). A central core imaging laboratory will collect and evaluate all DXA scans for acceptability, and will have bone mineral density assessed as per the imaging charter. Data from the DXA scans will be managed and analyzed separately by the core laboratory and integrated into the study's database at the end of the study. Bone mineral density changes for individual subject will be monitored by a central radiology laboratory over the course of the study.

Patients who experience a bone mineral density loss from the parent study Baseline of $\geq 7\%$ at any of the anatomical sites assessed will be discontinued from the extension study. Patients should be assessed for secondary causes of bone loss if determined necessary by the investigator and followed up to resolution if bone mineral density loss is determined by the investigator to be related to study drug.

At Week 52 or an Early Termination visit occurring on or after Week 36, patients with a bone mineral density loss of $> 3\%$ at lumbar spine or total hip relative to parent study Baseline measurement will undergo another bone densitometry scan at 6 (± 1) months and will be contacted to obtain information about medications and conditions (eg, pregnancy) that might

affect bone mineral density through the time of the follow-up bone densitometry. If Early Termination occurs prior to Week 36, follow-up bone densitometry will be performed according to the requirements of the parent study. The follow-up bone densitometry will be submitted for central reading.

If the patient enrolls directly into another relugolix clinical study upon completion of the Week 52 visit, then the follow-up bone densitometry scan at 6 (\pm 1) months conducted under this protocol may be waived.

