Clinical laboratory data consist of chemistry, hematology, and hormonal tests. Only data collected by the central laboratory will be used to do the analyses. ECGs will also be read centrally. The distributions of QTc interval will be summarized at each visit. All data will be listed and summarized by visit. The change from parent study Baseline to each post-baseline study visit will be presented by treatment group for each ECG parameter.

The incidence of vasomotor symptoms as assessed through adverse event reporting will be summarized by the parent study treatment arm.

Bone mineral density data will be collected and analyzed by the central radiology laboratory including bone mineral content (g), bone area (area, cm²), and bone mineral density (g/cm²) each for L1, L2, L3, L4, total hip, and femoral neck, and average bone mineral density of L1-L4 (lumbar spine), Z-score for bone mineral density lumbar spine (L1-L4), total hip, and femoral neck.

For the relugolix add-back treatment Group A, the lower bound of the 95% CI for (arithmetic) mean percentage change at Week 52 from parent study Baseline in bone mineral density lumbar spine (L1-L4) will be compared with a pre-specified clinically acceptable threshold of -2.2% to evaluate magnitude of bone mineral density loss after 52 weeks of treatment. If the lower bound is > -2.2%, the bone mineral density loss for the relugolix add-back treatment will be considered insignificant. As supportive analysis, least square means and 95% CI for % change at Week 52 from parent study Baseline in bone mineral density will be provided based on mixed effects model (assumed missing at random) for each parent study treatment group.

All data will be listed and summarized by visit. The change, percent change from parent study Baseline to Weeks 36 and 52 and associated 95% CIs will be presented by the parent study treatment group for each bone mineral density parameter. The number and percentage of patients meeting a bone mineral density decline of at least 4%, 5%, 6%, or 7% by body area (lumbar spine, total hip, or femoral neck) will be estimated with 95% CIs by the parent study treatment group.

Additional analyses will be performed to exam the correlation between bone mineral density loss with demographic and baseline characteristics and with treatment exposure. Details will be provided in the SAP.

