4.3.9. By-Visit Endpoints

By-visit endpoints will be analyzed using observed data, unless otherwise specified. For observed data analyses, missing data will not be imputed and only the observed records will be included.

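### The -2.2% spine rule uses the observed Week 52 mean, which leaves out women discontinued for a 7% loss, so it leans toward passing by an amount set by an SD the plan does not give

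*Protocol*

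**What the plan says.** Section numbers are those of the amended protocol, on which the SAP is based.

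- **Decision rule.** Protocol 9.5 sets the statistic, measured at the lumbar spine against parent Baseline: "For the relugolix add-back treatment Group A, the lower bound of the 95% CI for (arithmetic) mean percentage change at Week 52". It concludes: "If the lower bound is > -2.2%, the bone mineral density loss for the relugolix add-back treatment will be considered insignificant". The synopsis has the same comparison and describes the women concerned as those randomized to Group A who enrolled in the extension.
- **Removal rule.** Protocol 6.6.2.6 says that women with a loss of 7% or more from parent Baseline "at any of the anatomical sites assessed will be discontinued from the extension study". Protocol 4.5 lists the same event under an introduction that allows removal to be permanent or to last until the cause is found and resolved.
- **Scans.** Between entry and Week 52, the only scheduled DXA is at Week 36.
- **Visit assignment.** SAP Table 3 assigns Days 197-308 to Week 36 and Days 309-421 to Week 52. It excludes scans more than 30 days after the last extension dose.
- **Missing data.** SAP 4.1 imputes nothing unless stated. SAP 4.3.9 adds: "By-visit endpoints will be analyzed using observed data, unless otherwise specified".
- **Supportive analysis.** Protocol 9.5 also plans least squares means "based on mixed effects model (assumed missing at random) for each parent study treatment group". SAP 9.3.4 fits this model by group at Weeks 12, 24, 36 and 52. SAP 9.3.4 does not mention -2.2%.

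**The concern.** The rule is meant to describe all Group A women who enrolled. Its statistic describes those who still have a scan in the Week 52 window. Women discontinued for a large measured loss are missing from it because of that loss, so the lower tail of the distribution is thinned before the mean is taken.

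The error has one direction: the observed mean looks better than the mean for enrolled women. It also grows as large losses become more common, which is when the rule should be hardest to pass. This is the study's only pass/fail criterion, and it carries the 52-week bone-safety conclusion.

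**Working it through.** **1. Can a removed woman still have a Week 52 value?** The Week 36 target is Day 253. A Week 52 value needs a scan on or after Day 309, no more than 30 days after the last dose, so dosing must run to at least Day 309 - 30 = 279. That is 26 days past the Week 36 target. A woman stopped promptly on her Week 36 result does not meet this, and a termination scan before Day 309 counts as Week 36.

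**2. Figures in the plan.** The only planning figure is about 600 participants as 75% of 780: 0.75 x 780 = 585, which fits "about 600". No SD, Group A size or error rate is given for the rule. The lower limit of a two-sided 95% interval implies a pass rate of 1 - Φ(1.96) = 2.5% when the true mean is exactly -2.2%.

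**3. Assumptions, none from the documents.**
- 200 Group A women (600 / 3) and 15% random dropout.
- Normal percent changes at Weeks 24, 36 and 52, with means at 0.45, 0.70 and 1.00 of the Week 52 mean and SDs at 0.85, 0.92 and 1.00 of the Week 52 SD.
- Correlation between adjacent scans 0.70-0.85.
- Women at or below -7% at Week 24 not enrolled, as the exclusion criteria require, and the mean reset so that enrolled women average -2.2% at Week 52.
- Women at or below -7% at Week 36 have no Week 52 value.

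**4. Formula.** If removal raises the observed mean by b, and the standard error is SE = s/√m (s = SD of those left, m = number scanned), then pass rate ≈ Φ(b/SE - 1.96). For spine-only removal at correlation 0.70:

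| SD | Removed | b (points) | m | SE | Φ(b/SE - 1.96) |
|---|---|---|---|---|---|
| 2 | 0.14% | 0.007 | 200 x 0.85 x 0.9986 = 170 | 1.99/√170 = 0.153 | Φ(-1.91) = 2.8% |
| 3 | 2.0% | 0.101 | 200 x 0.85 x 0.980 = 167 | 2.91/√167 = 0.225 | Φ(-1.51) = 6.5% |
| 4 | 5.4% | 0.304 | 200 x 0.85 x 0.946 = 161 | 3.75/√161 = 0.296 | Φ(-0.93) = 17.6% |

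**5. Simulated pass rates at a true mean of -2.2%,** over correlations 0.70-0.85:

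| SD | Observed mean, spine triggers removal | Observed mean, any of three sites triggers | Missing-at-random estimate |
|---|---|---|---|
| 2 | 2-3% | 4-5% | 2-3% |
| 3 | 6-7% | 8-10% | 2-3% |
| 4 | 17-19% | 20-23% | 2-3% |

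The three-site column also assumes hip SD 2.5%, femoral neck SD 3.5% and cross-site correlation 0.5. Other reasonable choices for the hip and neck move it up by a point or two. The last column uses each woman's Week 24 and Week 36 spine values and holds even when the hip or neck triggers removal.

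**The case against.** **Size.** A reader might infer that the rule passes several times too often. The documents do not support that as a fact, because the answer turns on an unstated SD. At SD 2 with spine-only removal there is no material inflation, and at SD 2.5 the rate is about 4%. The higher three-site figures rest on further assumed inputs. This objection stands; only the direction follows from the documents.

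**Formal status.** A reader might also treat this as a failed hypothesis test. Neither document states a null hypothesis or an error rate for the rule, SAP 2.2 says no formal testing is planned, and the -2.2% comparison does not appear in the SAP. This also stands, so the 2.5% is only what the interval implies. Even so, the protocol draws a yes/no conclusion from the interval, and SAP 4.2, which openly departs from the protocol on populations, does not withdraw the rule.

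**Already visible.** The mixed model, the counts of women with declines of at least 4, 5, 6 or 7%, and the reasons for discontinuation are all planned. A gap between the plain mean and the model would show. What remains is that the conclusion is tied to the estimate with the bias.

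**Target.** Protocol 9.5 speaks of loss after 52 weeks of treatment, and the model estimates what removed women would have shown had they continued. Neither document settles how removal should be handled. The synopsis wording about enrolled women favours including them.

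**The remedy's performance.** Normal data with removal driven by recorded values suit a missing-at-random model. The planned model is fitted site by site, so a hip or neck trigger lies outside the spine model. The simulated rate stayed near 2-3% with such triggers, but under these assumptions only.

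**Conclusion.** The concern holds in a limited form. For the women the synopsis names, the observed Week 52 mean is biased toward meeting the -2.2% criterion, because a measured loss of 7% or more normally takes a woman out of it. That follows from the protocol and SAP together. The entry exclusion at Week 24 does not remove the effect; every figure above already applies it.

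The size is conditional on the assumptions listed: from negligible at SD 2 with spine-only removal to roughly eight or nine times 2.5% at SD 4 with three-site removal (20/2.5 = 8; 23/2.5 = 9.2). The calculation treats every removal as permanent, as 6.6.2.6 reads. If some women resume treatment, as 4.5 allows, and are scanned in the Week 52 window, the bias is smaller. A cheap improvement is justified. The removal rule itself is not in question.

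**What to change.** - In protocol 9.5 and the synopsis, base the -2.2% comparison on the lower 95% bound of the Group A Week 52 lumbar-spine least squares mean. Take it from the repeated-measures model already planned, include every enrolled Group A woman with any post-Baseline scan, and set covariates at their observed distribution.
- Add that comparison to SAP 9.3.4, which omits the rule.
- Keep the observed arithmetic mean and its interval as supportive. Beside it, give the number of Group A women with no Week 52 scan because of the 7% rule, and their last on-treatment values.
- Reconcile protocol 4.5 and 6.6.2.6 on whether removal for a 7% loss is permanent, since this determines who can have a Week 52 value.

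The cost is wording; no new model, scan or data collection is needed. The Week 52 estimate may be slightly less favourable, and the conclusion will rest on the missing-at-random assumption.

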9.6. Pharmacodynamic Analyses

The change from the parent study Baseline to Week 52 in pre-dose concentrations of serum estradiol will be summarized. Percentage of patients with concentrations of serum estradiol levels < 10 pg/mL and < 20 pg/mL will be provided.

9.7. Exploratory Analyses

Descriptive summaries by treatment group and between treatment group comparisons (when applicable) will be provided for the following exploratory endpoints. Details on the endpoint analyses including deviations, handling of missing data, and statistical methods will be provided in the SAP. The following exploratory endpoints will be assessed:

- Change from parent study Baseline to Week 52 in the European Quality of Life Five-Dimension Five-Level scale.

10. RESPONSIBILITIES

10.1. Investigator Responsibilities

10.1.1. Good Clinical Practice

The investigator will ensure that this study is conducted in accordance with the principles of the “Declaration of Helsinki” (as amended in Edinburgh, Tokyo, Venice, Hong Kong, and South Africa), International Council on Harmonisation (ICH) guidelines, or with the laws and regulations of the country in which the research is conducted, whichever affords the greater protection to the study participant. For studies conducted under a US investigational new drug application, the investigator will ensure that the basic principles of “Good Clinical Practice,” as outlined in 21 Code of Federal Regulations (CFR 312), subpart D, “Responsibilities of Sponsors and Investigators,” 21 CFR, part 50, 1998, and 21 CFR, part 56, 1998, are adhered to. These standards are consistent with the requirements of the European Community Directive 2001/20/EC.

Since this is a “covered” clinical study, the investigator will ensure that 21 CFR, Part 54, 1998, is adhered to; a “covered” clinical study is any “study of a drug or device in humans submitted in a marketing application or reclassification petition subject to this part that the applicant or FDA relies on to establish that the product is effective (including studies that show equivalence to an effective product) or that make a significant contribution to the demonstration of safety.” This requires that investigators and all sub-investigators must provide documentation of their financial interest or arrangements with the sponsor, or proprietary interests in the drug being studied. This documentation must be provided before participation of the investigator and any sub-investigator. The investigator and sub-investigator agree to notify the sponsor of any change in reportable interests during the study and for 1 year following completion of the study.

10.1.2. Institutional Review Board/Independent Ethics Committee Approval

This protocol and any accompanying material to be provided to the patient (such as advertisements, patient information sheets, or descriptions of the study used to obtain informed consent) will be submitted by the investigator to an IRB or IEC. Approval from the IRB or IEC must be obtained before starting the study and should be documented in a letter to the investigator specifying the protocol number, protocol version, protocol date, documents reviewed, and date on which the committee met and granted the approval.

Any modifications made to the protocol after receipt of IRB or IEC approval must also be submitted to the IRB or IEC for approval before implementation.

10.1.3. Informed Consent

The investigator is responsible for obtaining written informed consent from each individual participating in this study after adequate explanation of the aims, methods, objectives, and potential hazards of the study and before undertaking any study-related procedures. The investigator must utilize an IRB- or IEC-approved informed consent form for documenting written informed consent that contains all elements required by national, state, local, and institutional regulations or requirements. Each informed consent form will be appropriately signed and dated by the patient.

10.1.4. Confidentiality

The investigator must assure that patients' anonymity will be strictly maintained and that their identities are protected from unauthorized parties. Only patient number, date of birth, and an identification code (ie, not names) should be recorded on any form or biological sample submitted to the sponsor, IRB or IEC, or laboratory. The investigator must keep a screening log showing codes, names, and addresses for all patients screened and for all patients enrolled in the study.

The investigator agrees that all information received from the sponsor, including but not limited to the investigator brochure, protocol, eCRFs and other study forms, the investigational drug, and any other study information, remain the sole and exclusive property of the sponsor during the conduct of the study and thereafter. This information is not to be disclosed to any third party (except employees or agents directly involved in the conduct of the study or as required by law) without prior written consent from the sponsor. The investigator further agrees to take all reasonable precautions to prevent the disclosure by any employee or agent of the study site to any third party or otherwise into the public domain.

10.1.5. Steering Committee

The study will be overseen by a Steering Committee consisting of experts in the field of women's health and staff members of Myovant Sciences GmbH. The Steering Committee will participate in the design, conduct, analyses, and publication of the study.

10.1.6. Study Files and Retention of Records

The investigator must maintain adequate and accurate records to enable the conduct of the study to be fully documented and the study data to be subsequently verified. These documents should be classified into at least the following two categories:

1. Investigator's study file. The investigator's study file will contain the investigator brochure, protocol/amendments, IRB or IEC and governmental approval with correspondence, informed consent forms, drug records, staff curriculum vitae, authorization and training forms, and other appropriate documents and correspondence.
2. Patient clinical source documents. The required source data should include the following for each patient:
 - a. Patient identification (name, date of birth, gender);
 - b. Documentation that the patient meets eligibility criteria, (eg, history, physical examination, and confirmation of diagnosis to support inclusion and exclusion criteria);
 - c. Participation in the study (including study number);
 - d. Study discussed and date of informed consent;
 - e. Dates of all visits;
 - f. Documentation that protocol-specific procedures were performed;
 - g. Results of efficacy parameters, as required by the protocol;
 - h. Start and end date (including dose regimen) of study medication (drug dispensing and return should be documented as well);

-
- i. Record of all adverse events and other safety parameters (start and end date, and causality and intensity as assigned by the investigator);
 - j. Concomitant medication (including start and end date); and
 - k. Date of study completion and reason for early discontinuation, if applicable.

All clinical study documentation must be retained by the investigator until at least 2 years after the last approval of a marketing application in an ICH region (ie, United States, Europe, or Japan) and until there are no pending or contemplated marketing applications in an ICH region; or, if no application is filed or if the application is not approved for such indication, until 2 years after the investigation is discontinued and regulatory authorities have been notified.

Investigators may be required to retain documents longer if required by applicable regulatory requirements, by local regulations, or by an agreement with the sponsor. The investigator must notify the sponsor before destroying any clinical study records.

Clinical study documentation includes the investigator brochure, signed protocol and amendments, signed informed consents, notification of serious adverse events and related reports, any dispensing and accountability logs, shipping records of investigational product and study-related materials, documentation of financial aspects of the study, insurance statement, and signed agreement between the involved parties, dated and documented IRB/IEC approval, approval of regulatory authorities as applicable, decoding procedures for blinded studies, curriculum vitae and all training records of study site personnel, and all correspondence pertaining to the conduct of the study.

Should the investigator wish to assign the study records to another party or move them to another location, the sponsor must be notified in advance.

If the investigator cannot guarantee this archiving requirement at the study site for any or all of the documents, special arrangements must be made between the investigator and the sponsor to store these in sealed containers outside of the site so that they can be returned sealed to the investigator in case of a regulatory audit. When source documents are required for the continued care of the patient, appropriate copies should be made for storage outside of the site.

